2. OBJECTIVE

2.1 Primary Objective:

To examine differences in dose reductions, dose delays and early stoppage for chemotherapy and the total combined number of moderate and severe chemotherapy-associated toxicities between intervention group and waitlist controls.

2.2 Secondary Objectives:

2.2.1 Examine specific inflammatory markers (CRP, IL-6, TNF- α receptor II [TNF-RII]) in relation to baseline MM and FM and examine differences in changes in inflammatory markers between intervention group and waitlist controls.

2.2.2 Examine the impact of intervention versus control and RT-induced body composition changes on the pharmacokinetics [PK] of 5-FU and oxaliplatin between baseline and 4 months of RT.

2.3 d3 Creatine Objectives:

2.3.1 Test whether resistance training during chemotherapy (FORCE intervention group v. control) increases d3 creatine muscle mass at 6 months.

2.3.2 Evaluate the association of d3 creatine muscle mass with changes in functional status and strength during chemotherapy.

2.3.3 Evaluate the association of d3 creatine muscle mass with chemotherapy toxicity and relative dose intensity.

2.3.4 Evaluate the association of d3 creatine muscle mass with cancer-related biomarkers, including inflammation, CEA levels and cardiometabolic risk factors.

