			Day 1																												28 Weeks															
sLV5FU2 Leucovorin, followed by 2 day continuous infusion 5FU, repeated every 2 weeks	2 days	12 cycles	IV		IV		IV		IV		IV		IV		IV		IV		IV		IV		IV		IV		IV																			
			Day 1																				20 Weeks																							

INTERVENTION
DRUG
VISIT

A research assistant will either conduct eConsent over the phone or by video conference or meet the participant in person to complete the consent forms. The baseline visit will most likely occur as an add-on to the first or second chemotherapy infusion session or another clinical appointment, so as to avoid the need for additional visits to the clinic or cancer center for the study. If scheduling of the baseline or follow-up visits at the clinic is not convenient for the participant, the research assistant will also be available to conduct these study visits at the participant's home.

After the participant consents to be in the study (see Appendix 13.3), we will complete questionnaires with the participant as part of the baseline visit (e.g. physical activity assessment and physical function testing, see Appendix 13.5, FFQ, see Appendix 13.6.1, SF-36, and demographics, see Appendix 13.4), as well as a patient-completed side effects questionnaire

(see Appendix 13.7.3). In addition, body composition will be assessed using anthropometrics collected at the baseline visit, a DXA (see Appendix 13.8) to be scheduled as soon as possible, prior to initial intervention, and creatine dilution (see Appendix 13.8.3). Also, at the baseline visit, we will arrange for research blood draw, when possible to be coordinated with clinical blood draw that the patient receives as part of clinical care (either that visit or next chemotherapy visit but prior to starting intervention).

3.8 Interventions for experimental group:

Table 4. Intervention Terminology

Chemotherapy Cycle	A cycle of chemotherapy from infusion visit to the next infusion visit, usually this will be 2-3 weeks
Chemotherapy Infusion Visit	Date on which the participant receives chemotherapy infusion at the cancer/medical center.

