4. STUDY MEASUREMENTS

Initial screening will take place via telephone. At the in-person baseline visit, after the patient signs the consent form, s/he will undergo a series of baseline assessments, questionnaires and blood draws as described above. Many of the data collection instruments will be either data entered by a researcher or self-administered by participants into REDCap, which is a secure web application for managing online surveys and databases. The table below provides an overview of the measurements that participants will undergo over the course of the protocol and the timing of these measurements:

Table 7. Measurement Schedule

Measure	Screening	Baseline	Weekly	PK Cohort Only	Post-Intervention Visit ³
Phone screening questions- PA screening and additional questions	X				
PAR-Q	X				
SF-36 ⁴		X			X
Demographics ⁴		X			
Paffenbarger questionnaire		X			X
Physical function tests (balance, gait speed, sit and stand, grip strength)		X			X
Food frequency questionnaire ⁴		X			X
Height, weight, waist and hip circumference		X			X
Whole body DXA		X		X ²	X
Patient-completed side effects questionnaires ⁴		X			X
D3- creatine dilution		X			X
NCI PRO CTCAE			X ¹		
Medical record review for chemotherapy dosing and toxicities			X		
Physical activity and nutrition logs			X		
Inflammatory markers		X			X
Pharmacokinetics (PK)				See section 4.14	
Injury history questionnaire ⁴					X
Intervention follow-up survey					X

¹ At each scheduled intervention visit (for intervention arm) and thereafter by phone or secure web-link every time chemotherapy appointment is scheduled. For U group controls, an RA will administer by phone or secure web-link every time a chemotherapy appointment is scheduled.

² For PK cohort, a DXA scan will also occur at time of 2nd PK draw, at approximately 4 months after initiation of the intervention

³ To be conducted within 2 weeks after last cycle of chemotherapy and end of intervention

⁴ As a result of COVID-19, to reduce in person time participants will complete baseline and post-intervention questionnaires virtually. Study staff will email participants a secure web-link, send them home with paper copies to be mailed back within 3 days, or administer questionnaires over the phone.

4.1 Screening questionnaire:

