Details of each patient's health history, including medical imaging, comorbidities and colon cancer diagnosis and treatment details will be extracted from the EMR. In addition, laboratory and clinical data about the colon cancer tumor marker Carcinoembryonic Antigen (CEA) and cardiometabolic risk factors blood glucose, lipids, blood pressure and medication usage conditions will be extracted from the EMR. See Appendix 13.2.1. A researcher will record all relevant medical variables in an online REDCap form. In addition, CT scans will be obtained from the participant's medical record. KP scans will be stripped of PHI and analyzed at DOR. Penn State and DFCI scans will be stripped of PHI and transmitted directly to DOR via SFT. CT scan closest to the date of diagnosis but before chemotherapy will be colored using TomoVision sliceOmatic software to determine body composition, including muscle attenuation.

4.10 Body composition and body size:

At the baseline visit and at the follow-up visit, a DXA scan to assess body composition will be performed (see Appendix 13.8.2). All DXA scans will be performed in the total body scanning mode. A third scan will take place after 4 months for the subset of people participating in the PK study to correspond to timing of the 2nd PK blood draws.

At the baseline visit and at the follow-up visit, d3-creatine dilution will be used to accurately assess total body skeletal muscle mass (see Appendix 13.8.3).

Height and weight will be assessed using a scale mounted stadiometer and digital scale (or per institutional clinic standards) to the nearest 0.1 cm and 0.1 kg. Waist circumference and hip

circumferences will be measured at standardized landmark with participants dressed in light indoor clothing without shoes. Height will be assessed at baseline only. A researcher will record anthropometric measurements in an online REDCap form. See Appendix 13.8.1.

Because of COVID-19, if a participant doesn't feel comfortable with study staff touching him/her for waist or hip circumference measures, the study staff can teach the participant how to self-measure while observing and recording results in REDCap.

4.11 Dose reductions/delays and early discontinuation of treatment:

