At the initiation of adjuvant chemotherapy, we will ascertain planned treatment course for participants, including planned cumulative dose and planned treatment duration. We will then examine the EMR for changes in chemotherapy dose and timing. The following variables will be defined for each drug administered:

- Planned dose intensity (mg/week) = planned total dose / planned duration of therapy (weeks)
- Actual dose intensity (mg/week) = actual total dose (mg) / actual duration of therapy (weeks)
- Relative dose intensity (RDI) (%) = actual total dose intensity / planned total dose intensity
- Average relative dose intensity (ARDI) (%) = the average across all regimens of the relative dose intensity
- Number of cycles of chemotherapy and date of initiation of each cycle

In addition, we will report on early stoppage by calculating actual number of cycles / planned number of cycles of adjuvant therapy. We will only consider dose reductions that occur after start of intervention. Chemotherapy treatment forms will be used to capture data from the EMR on chemotherapy administration (see Appendix 13.7.4). A researcher will record all relevant chemotherapy treatment variables in an online REDCap form.

4.12 Chemotoxicity:

Total combined number of moderate and severe chemotherapy-associated toxicities, assessed via medical record review, patient-completed NCI PRO-CTCAE and patient-completed side effects questionnaires. As shown in the Appendix, we will use a series of validated questionnaires for chemotherapy-associated side effects including NCI PRO-CTCAE and a questionnaire on neurotoxicity utilized in a recent phase III trial with oxaliplatin⁴⁸. See Appendix 13.7. Throughout the intervention, the research manager or assistant will email a secure web-link to the patient requesting completion of the NCI PRO-CTCAE questionnaire in advance of his/her next chemotherapy infusion visit. A researcher will record all relevant chemotoxicity variables in an online REDCap form. Participants will complete the patient-completed side effects questionnaire and NCI PRO-CTCAE questionnaire in online REDCap surveys.

4.13 Inflammatory blood measures:

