set of potential confounders for cross-sectional analyses at baseline includes age, sex, body mass index or weight, race/ethnicity and tumor stage. For longitudinal analyses, potential confounders also include chemotherapy type, intervention assignment and time from surgery and/or chemotherapy start to assessment. We will include those covariates resulting in a 10% or more change in the d3 creatine muscle mass regression coefficient. The change-in-estimate approach to confounder selection performs well with regard to power, bias, mean squared error and confidence interval coverage.

9.3.4 Power:

Given previous exercise studies in cancer patients, we assume approximately 10% drop out with no follow-up DXA and blood draw for biomarker assessment. We expect chemotoxicity metrics (RDI, # toxicities) to be assessed on the full sample. We have sufficient power (.80) to detect a between arm difference in means of at least .42 standard deviation (s.d.) units (two-sided t-test, $\alpha=.05$) in Aim 1 analyses of chemotoxicity. With an expected RDI s.d. of 17.3⁴⁵, the minimum detectable difference in mean RDI is 7.3%, which is clinically meaningful and similar to effects found with a study of exercise among breast cancer patients receiving adjuvant chemotherapy⁴⁵. With the expected loss to follow-up and reduced sample size of 81 per group, the minimum detectable between arm difference in mean change is .44 units, which is considered in the “small” to “medium” range in effect size using the terminology and classification of Cohen. Relevant to Aim 4, on pharmacokinetics, a sample size of 30 subjects will provide sufficient power (.80) to detect a mean change of at least 0.5 s.d. units (two-sided t-test, $\alpha=.05$). Given previous data²⁶, the minimum detectable change in clearance of oxaliplatin or 5-FU due to RT is 15%.

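### Protocol 9.3.3 leaves "assessment" undefined in a candidate time covariate, so d3-creatine models for RDI and toxicity may condition on treatment length received

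*Protocol*

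**What the plan says.** Objective 2.3.3 of the protocol is to "Evaluate the association of d3 creatine muscle mass with chemotherapy toxicity and relative dose intensity". Section 9.3.3 lists RDI among the continuous outcomes for linear regression and accepts that the association aims (2 to 4) are open to confounding. It gives one candidate list for cross-sectional models at baseline and then extends it: "For longitudinal analyses, potential confounders also include chemotherapy type, intervention assignment and time from surgery and/or chemotherapy start to assessment". The selection rule is: "We will include those covariates resulting in a 10% or more change in the d3 creatine muscle mass regression coefficient".

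The measurement times are set elsewhere in the protocol:

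- Section 4.10: "At the baseline visit and at the follow-up visit, d3-creatine dilution will be used to accurately assess total body skeletal muscle mass".
- Section 3.7, baseline: "The baseline visit will most likely occur as an add-on to the first or second chemotherapy infusion session".
- Table 7, footnote 3, post-intervention visit: "To be conducted within 2 weeks after last cycle of chemotherapy and end of intervention".
- Objective 2.3.1 instead speaks of whether training "increases d3 creatine muscle mass at 6 months".

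On the outcomes, Protocol 4.11 divides actual total dose by actual duration of therapy. SAP 1.1 counts missed cycles and states that its RDI takes in reduction, delay and early stoppage. Protocol 4.12 defines toxicity as a total count. Planned duration (3 or 6 months) is a minimization factor in Protocol 9.1 and a covariate in the SAP 2.2 primary models, but it is not in the 9.3.3 list.

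**The concern.** A confounder should precede the outcome. Time from chemotherapy start to a visit fixed by the last cycle does not: it is planned length, less early stoppage, plus delay, plus up to two weeks. Protocol 1.5 sets out the hypothesis that low muscle mass raises toxicity enough to force reductions, delays or termination. On that hypothesis, treatment length received lies on the pathway under study. For RDI it also holds components of the outcome. For toxicity it is not a component of the count; it is time at risk and may itself be shortened or lengthened by toxicity.

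The change-in-estimate rule gives no protection, because a mediator or an outcome component moves the coefficient just as a confounder does. Planned duration, the pre-treatment variable that the term partly stands in for, is not offered. Chemotherapy type does not supply it either, since Table 3 lists both mFOLFOX6 and CAPEOX in 3- and 6-month forms. At stake is whether the 2.3.3 estimates describe the association of muscle mass with RDI and toxicity, or an association within levels of treatment already received.

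**Working it through.** The documents give no figure for these models, so there is none to reproduce.

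**Step 1: how the term relates to RDI.** Take 12 planned two-week cycles (24 weeks) at one dose unit per cycle. Planned intensity is 12/24 = 0.50. For simplicity everything is counted from chemotherapy start.

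| Course | RDI by Protocol 4.11 | RDI with missed cycles counted | Chemotherapy start to follow-up visit |
|---|---|---|---|
| As planned | (12/24)/0.50 = 100% | 100% | 24–26 weeks |
| Stops after 8 full-dose cycles | (8/16)/0.50 = 100% | 8/12 = 67% | 16–18 weeks |
| All 12 cycles, 4 weeks of delay | (12/28)/0.50 = 86% | 86% | 28–30 weeks |

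A low RDI can go with a short or a long time to the visit, so the bias has no fixed sign. Under 4.11, early stoppage at full dose leaves RDI at 100%, so the size also depends on the formula.

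**Step 2: simulation by mechanism (all effects assumed).** There were 180 patients per run and 500 runs per scenario.

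- Half had 6 and half had 12 planned two-week cycles.
- The baseline visit fell 0–2 weeks after chemotherapy start, and follow-up 0–2 weeks after treatment ended.
- At average muscle mass the stopping probability was 1/(1+e^1.2) = 23%, mean delay 1.5 weeks per 12 planned cycles, and dose reduction about 5%.
- In the strong mix, one SD more muscle mass lowered the log-odds of stopping by 0.6, log mean delay by 0.4 and dose reduction by 4 percentage points. The weaker mix halved these effects.
- The single-mechanism scenarios used the 0.6 or the 0.4 alone.
- RDI with missed cycles counted = 100 × (dose given/planned cycles) × planned weeks/(planned weeks + delay).

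The table gives the mean muscle-mass coefficient for that RDI. Percentages come from unrounded values and compare with the model without covariates.

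| Muscle mass acts through | No covariate | Time to follow-up alone | Planned duration + time to follow-up | Planned duration + time to baseline |
|---|---|---|---|---|
| Stopping only | 3.28 | 2.73 (-17%) | 1.00 (-69%) | 3.28 (0%) |
| Delay only | 1.96 | 2.36 (+20%) | 3.53 (+81%) | 1.96 (0%) |
| Strong mix | 7.66 | 7.51 (-2%) | 7.07 (-8%) | 7.65 (0%) |
| Weaker mix | 3.93 | 3.84 (-2%) | 3.54 (-10%) | 3.93 (0%) |

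Time to follow-up alone met the 10% rule in 72%, 73%, 9% and 36% of runs. With planned duration also in the model the figures were 100%, 95%, 48% and 70%. For the 4.11 RDI, the mean shift was at most 3% in three scenarios. With stopping only it was +9% (+27% with planned duration), on a coefficient of only 0.31.

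**Step 3: cycle-by-cycle simulation including toxicity (also assumed).** Two-week cycles, 6 or 12 planned; toxicity in about 35% of cycles; per cycle about 3% stop, 15% have a one-week delay and 5% a 20% dose reduction; log-odds of toxicity lower by 0.3–0.5 per SD of muscle mass; 60,000 patients per setting. With the actual-time term in a mixed 3/6-month sample, the coefficient moved by -6% to -11% for RDI with missed cycles counted (-21% to -24% with planned duration also in the model), +5% to +13% for the 4.11 RDI and +6% to +11% for the toxicity count.

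A further mixed-mechanism simulation, also on assumed effects, gave about -8%, +2% and +6% for the same three outcomes. The 10% rule was met in about 62%, 20% and 51% of samples of 162 (2 × 81, the number expected at follow-up in Protocol 9.3.4).

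**The case against.** The strongest reply is that the sentence has a harmless reading. RDI is taken from the medical record, not measured at the follow-up visit, and the d3 measurement that precedes RDI and toxicity is the baseline one. Time from surgery or chemotherapy start to that visit is a legitimate covariate. This stands: the text does not settle which visit is meant. Adding the term only for longitudinal models leans towards follow-up but does not prove it.

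A reader might infer that the plan does adjust RDI and toxicity for treatment length received. The documents do not support that, because the term is a candidate under the 10% rule. Nor is the visit date wholly fixed by the last cycle. Objective 2.3.1 says 6 months, Protocol 3.8 puts the end of the intervention at about 6 months, and Section 7 asks patients removed after choosing to stop chemotherapy for follow-up where feasible, without a timing rule.

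A reader might also infer a large bias of known direction. The largest shifts need a single mechanism or planned duration in the model, and 9.3.3 does not list planned duration.

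Finally, the same list serves objectives 2.3.2 and 2.3.4, where elapsed time can be a reasonable covariate for change in function, strength or biomarkers. The documents give no ground for removing it there. The randomized d3 comparison (2.3.1) and the SAP primary models are not affected.

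**Conclusion.** The concern holds conditionally, for objective 2.3.3 only. If the assessment is the follow-up visit and the term passes the 10% rule, the RDI model conditions on part of its outcome, and the toxicity model on exposure time that may be a consequence of toxicity. The rule would not reveal either problem. If baseline is meant, the sentence needs only clarification, plus planned duration.

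With the listed term alone and mixed stopping, delay and reduction, the simulated shift is about -2% to -11% for RDI with missed cycles counted, 0 to +13% for the 4.11 RDI and +6% to +11% for toxicity. Every one of these figures rests on assumed effects. They show that the distortion can be negligible or material and of either sign; they do not predict its size in this trial. The point is worth acting on because the stated rule can select a biased model and the remedy is cheap.

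**What to change.** In Protocol 9.3.3, for objective 2.3.3:

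1. Define the time term as running from surgery, and from chemotherapy start, to the baseline d3 assessment.
2. Add planned treatment duration (3 or 6 months) to the covariates.
3. State that models for RDI and toxicity will not adjust for time to the follow-up visit or for any other measure of treatment actually received.
4. If a toxicity rate is wanted rather than a count, name it as the estimand and enter exposure time as an offset.

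Elapsed time to follow-up may stay as a covariate for the change outcomes in 2.3.2 and 2.3.4. The 6-month wording of objective 2.3.1 and the visit rule in Table 7 should be reconciled at the same time.

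The cost is a few sentences. Planned duration is already recorded for minimization, and the baseline dates are available. The downside is slightly more residual variance in some models. In the step 2 simulation, planned duration plus time to baseline left the mean RDI coefficient unchanged in all four scenarios, under both RDI definitions.

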- Currently prescribed one of the following adjuvant chemotherapy regimens: (IV 5-fluorouracil [5-FU] / leucovorin [LV], capecitabine, FOLFOX [5-FU, LV, oxaliplatin], CAPOX [capecitabine and oxaliplatin]
 - Patients must have started chemotherapy or plan to start, with planned receipt of the first exercise visit **by the third infusion visit**.
 - Patients receiving FOLFOX chemotherapy are eligible to enroll in the pharmacokinetics sub-study (see section 3.10).
- No planned major surgery anticipated in the intervention period
- Sufficient time to heal from any major surgery to start of intervention, including colostomy reversal (port-a-cath removal excluded)
- Creatinine value < 2 mg/dL
- Approval by either oncologist or surgeon to participate in trial
- Readiness (as determined by the Physical Activity Readiness Questionnaire (PAR-Q) – see Appendix 13.2.2)
 - If there are any indications that home based exercise would be unsafe based on PAR-Q the patient will not be enrolled until confirmation from the patient's treating provider is received via email and/or phone that they are safe to exercise. Provider does not need to be contacted if patient answers 'yes' to 'Is your doctor currently prescribing any medication for your blood pressure or for a heart condition?'
- Ability to understand and the willingness to sign a written informed consent document in English
- Willingness to be randomized

3.4 Exclusion criteria:

- Concurrent actively treated other cancer (except non-melanoma skin cancer, in situ cervical cancer or localized prostate cancer treated with surveillance only)
- Patients with untreated hypertension (> 180 mm Hg systolic or > 100 mm Hg diastolic) appearing in the patient's medical record in the two weeks prior to screening will not be enrolled until confirmation from the patient's treating provider is received via email and/or phone that they are safe to exercise.
- Presence of metastatic disease
- Current strength training ≥ 2 x week for the past 3 or more months
- Patients enrolled in other clinical trials of weight loss, physical activity or dietary interventions are ineligible.

3.5 Inclusion of women and minorities:

We seek to recruit 180 participants with a diagnosis of colon cancer. We will not exclude any participants due to their race and ethnicity. All races are accepted. The distribution of

participants by race and ethnicity is expected to mirror that of the institution's colon cancer patient population.

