9.2.1 From Section D. Study overview of the original KPNC application approved 2017

3. How many participants will be enrolled in this study, or how many electronic records or medical records will be used? Provide your best estimate if you are not sure

Number of KPNC participants or records:	Approximately 115 participants to be enrolled
Records used:	Approximately 7500-KPNC records used
Number of non-KPNC participants or records:	Approximately 65 participants enrolled
Total number of participants or records:	Approximately 180* participants enrolled

**Due to the impact of the COVID-19 pandemic on the study, we estimate that the total number of participants will be within the range of 10% above the original total of 180 participants*

9.3 Statistical analysis:

9.3.1 Primary endpoints:

All data analyses will be by intent-to-treat, though in exploratory analyses we will consider compliance to intervention (defined as $\geq 75\%$ of planned sessions) and changes in MM. We will use multiple linear regressions to assess the difference between the intervention and wait-list control groups in mean relative dose intensity (RDI) for each agent and in mean average RDI (ARDI) across all agents. Continuous model covariates will be categorized either as quartiles or into clinically relevant categories (e.g. WHO BMI classification).

Analysis of number of grade 3 and 4 toxicities in relation to randomization arm will utilize Poisson regression given that this outcome can be characterized as a count. These regression models will provide point and interval estimates of adjusted proportional differences in rates of toxicities (expressed as rate ratios) between the control and intervention groups.

9.3.2 Secondary endpoints:

Analyses of inflammatory markers in relation to baseline body composition will utilize multiple linear regression techniques. These analyses of associations at baseline will be conducted in each randomization arm separately, followed by an analysis in the full sample (differences in associations at baseline across arms are not expected).

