## **DESCRIPTION OF PRIMARY ENDPOINTS**

### **1.1 Chemotherapy completion rates**

Relative dose intensity (RDI) will be calculated for each chemotherapy agent as well as average relative dose intensity (ARDI), which considers all chemotherapy agents in a regimen. We will examine differences in overall RDI for each chemotherapy agent and the ARDI across regimens between the RT group and the UC group.

RDI will be calculated as Delivered dose intensity (DDI) / Standard dose intensity (SDI). SDI will be calculated as the starting dose/m^2 multiplied by number of planned cycles by total number of days from day 1 of first cycle after randomization to last planned dose of that drug. DDI will be calculated as the sum total of dose/m^2 for each of the cycles that occur between randomization and follow-up, divided by total number of days from day 1 of first cycle after randomization to last actual dose of that drug. Calculation of DDI will include missed cycles similar to Weycker's method. Thus, our measure of RDI incorporates dose reduction/modification, treatment delay, and early stoppage.

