## **STATISTICAL CONSIDERATIONS**

### **2.1 Sample Size**

This study intended to randomize 180 colon cancer patients, with 90 in each treatment arm. In the end, due to missing data due to COVID, we randomized 183 participants, 92 to RT and 91 to UC. We expect chemotherapy dosing and completion rates (RDI, ARDI) to be assessed on all participants.

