### **2.2 Analysis of primary endpoints**

## Statistical Analysis Plan

FORCE: Focus on Reducing Dose-Limiting Toxicities in Colon Cancer with Resistance Exercise

All data analyses will be by intent-to-treat. Multiple linear regression will be used to assess the difference between the RT and UC groups in RDI. We will analyze RDI individually for each drug and then across all chemotherapy regimens combined. We will use logistic regression to examine the commonly used cut points < 85% and <70% RDI as outcomes.

We will assess the difference between RT and UC groups in self-reported treatment toxicities in three ways:

- A. as a binary variable with yes as the occurrence of any of one of 8 symptoms that are reported as moderate or severe over the course of chemotherapy in RT vs. UC. We will exclude the PRO-CTCAE muscle ache item from the composite score (will be reported separately), since that is believed to be related to the performance of the resistance training intervention. We'll utilize logistic regression for point and interval estimation of odds ratios, RT vs. UC, for any (i.e., one or more) of 8 symptoms reported as moderate severe, for each symptom individually, and finally in groups of similar symptoms, such as gastrointestinal issues;
- B. as the number of the 8 symptoms reported as moderate or severe at least once over the course of chemotherapy in RT v. UC (a count ranging from 0-8). We will use Poisson regression with allowance for overdispersion for point and interval estimation of relative differences (rate ratio) in the mean total number of moderate or severe toxicities reported at least once over the course of chemotherapy; and
- C. as longitudinal analyses of number of moderate or severe toxicities reported per cycle in relation to randomization arm (RT vs. UC) and time since randomization using Poisson regression with allowance for overdispersion. Generalized estimation equations (GEE) will be used for model parameter estimation to account for within person correlation in repeated measures. The main effect for randomization arm is interpreted as the average treatment effect over the time. Heterogeneity in effect over time will be assessed by inclusion of randomization arm by time-interaction terms.

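### The .80 power for a 7.3-point RDI difference in Protocol 9.3.4 needs all 180 patients, so it can hold for ARDI but not for every single-drug RDI analysis listed under primary endpoints

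*Protocol*

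**What the plan says.** Protocol 9.3.4 gives one power statement for RDI: "We have sufficient power (.80) to detect a between arm difference in means of at least .42 standard deviation (s.d.) units" (two-sided t-test, alpha .05), attached to the Aim 1 chemotoxicity analyses. With an expected SD of 17.3 it converts .42 SD into a minimum detectable difference of 7.3 points. The population is described just before: "We expect chemotoxicity metrics (RDI, # toxicities) to be assessed on the full sample". SAP 2.1 keeps that expectation and names both measures: "We expect chemotherapy dosing and completion rates (RDI, ARDI) to be assessed on all participants". It plans 90 per arm and reports 183 randomized (92 and 91).

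Both documents place single-drug RDI among the primary endpoints. Protocol 9.3.1 compares the arms "in mean relative dose intensity (RDI) for each agent and in mean average RDI (ARDI) across all agents". SAP 1.1 refers to "differences in overall RDI for each chemotherapy agent and the ARDI across regimens", and SAP 2.2 states: "We will analyze RDI individually for each drug and then across all chemotherapy regimens combined". Protocol 4.11 introduces the dose-intensity measures with: "The following variables will be defined for each drug administered".

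The eligible regimens in Protocol 3.3 are IV 5-FU/leucovorin and "capecitabine, FOLFOX [5-FU, LV, oxaliplatin], CAPOX [capecitabine and oxaliplatin". The regimen levels used for minimization in Protocol 9.1 are the same four. Neither document gives an expected regimen mix, or a sample size, SD or power for any single drug.

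**The concern.** Each eligible regimen is built on either 5-FU or capecitabine, never both. By planned regimen, therefore, 5-FU RDI and capecitabine RDI cannot both be analysed on the full sample, and the smaller group has at most half of it. Oxaliplatin also falls short of the full sample if any patients are planned for 5-FU/LV or capecitabine alone.

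The only RDI power figure uses every patient and is not limited to ARDI. A reader of 9.3.4 could therefore take a non-significant 5-FU or capecitabine result as coming from an analysis with .80 power to find 7.3 points. At half the sample the 95% confidence interval is wide enough that such a result often would not rule out a 7.3-point benefit.

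**Working it through.** **Inputs.** Two-sided alpha .05, t-test, difference 7.3 points and SD 17.3 (Protocol 9.3.4); 180 planned (Protocol 9.2), 90 per arm (SAP 2.1); 92 and 91 randomized (SAP 2.1); four eligible regimens (Protocol 3.3 and 9.1). Assumed here: the same SD for every drug, near-equal arms within each drug (planned regimen is a minimization factor), patients counted by planned regimen, and no allowance for degrees of freedom used by covariates.

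**Formula.** Standardized effect d = 7.3/17.3 = 0.422. Noncentrality = d / √(1/n₁ + 1/n₂), with n₁ + n₂ − 2 degrees of freedom. Power comes from the noncentral t distribution.

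**1. The protocol's own figure, 90 per arm.** Noncentrality = 0.422/√(2/90) = 2.83; critical t = 1.973; power = .804. The difference detectable with .80 power is 0.4199 SD × 17.3 = 7.26 points. This reproduces .42 SD and 7.3 points. About 89 per arm are needed for .80 at 7.3 points, so the figure uses the whole sample. With 92 and 91: power .810, detectable 7.20 points.

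**2. Upper limit for the less-used of 5-FU and capecitabine.** The two groups do not overlap by planned regimen, so the smaller has at most 180/2 = 90 patients, or 45 per arm. Noncentrality = 0.422/√(2/45) = 2.00; critical t = 1.987; power = .508. Detectable difference = 0.5972 × 17.3 = 10.33 points. With the 183 randomized (46 and 45): power .512, detectable 10.27 points.

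**3. The more-used drug.** It has between 45 and 90 per arm, so its power lies between .508 and .804.

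**4. Other shares of the 180 (assumed, since the documents give no split).**

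| Share on the drug | Per arm | Power at 7.3 points | Detectable at .80 (points) |
|---|---|---|---|
| 80% | 72 | .71 | 8.1 |
| 70% | 63 | .65 | 8.7 |
| 60% | 54 | .58 | 9.4 |
| 50% | 45 | .51 | 10.3 |
| 40% | 36 | .42 | 11.6 |
| 30% | 27 | .33 | 13.4 |
| 20% | 18 | .23 | 16.6 |

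The rows from 60% to 80% apply equally to oxaliplatin at those shares.

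**5. Sensitivity at 45 per arm (assumed inputs).** Covariates explaining a fraction R² of the variance multiply d by 1/√(1 − R²): R² = .10 gives power .55 and R² = .20 gives .60. Changing the SD instead: 15 gives .63 and 20 gives .40. Both SD 15 and R² = .20 give .72. Reaching .80 would take an SD of about 12.2, equivalent to R² = 1 − (12.2/17.3)² ≈ .50.

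**6. What a non-significant result would exclude.** The 95% CI half-width is t × 17.3 × √(2/n): 5.09 points at 90 per arm and 7.25 at 45. By simulation (normal data, SD 17.3, 2,000,000 draws per case), the share of non-significant results whose interval still contains +7.3 points is:

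| True effect (points) | 45 per arm | 90 per arm |
|---|---|---|
| 0 | 49% | 18% |
| 2 | 68% | 40% |
| 3.65 | 80% | 59% |

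**The case against.** The strongest reply is that the full-sample wording is about missing data. In 9.3.4 it follows the 10% drop-out allowance for DXA and blood draws, and contrasts visit-based outcomes with outcomes taken from records. SAP 2.1 likewise follows a remark on data lost to COVID. Read that way, every participant contributes an RDI for the drugs in their regimen and an ARDI, and SAP 2.1 is not false. This stands, and it is why SAP 2.1 needs clarifying rather than retracting. It does not extend the .80 to single drugs, because .42 SD needs about 90 per arm whatever the reason for expecting complete data.

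A second reply is that 9.3.4 never mentions each agent, and SAP 2.2 uses RDI both for single drugs and for the regimens combined, so the power may have been meant for ARDI. That is possible. But 9.3.4 names RDI, which Protocol 4.11 defines drug by drug, and SAP 2.1 lists RDI and ARDI separately. If ARDI was meant, the text should say so.

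Third, a reader might infer that the planned single-drug analysis would miss a true 7.3-point effect at least 49% of the time. The documents do not support that as a floor. SAP 2.2 adjusts every model for site, treatment duration, regimen, gender and stage, and the SD for a single drug is unknown; step 5 shows power moving both ways. The SD itself cannot be checked from the documents: its citation number leads, in the reference list, to a paper on the accuracy of a physical activity questionnaire, and nothing shows whether 17.3 describes one drug or an average.

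Fourth, switching between 5-FU and capecitabine during treatment could create some overlap. The half-sample limit is by planned regimen only.

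Finally, randomization is complete, so restating power cannot change the design, and reported confidence intervals will show the precision actually obtained. That limits the consequence but leaves the stated scope wrong.

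**Conclusion.** The point holds as an error of scope in the power statement. The .80 at 7.3 points is correctly computed for 90 per arm and can stand for ARDI, provided SD 17.3 applies to ARDI. It cannot hold for every single-drug RDI analysis listed under primary endpoints. Under 9.3.4's own assumptions, the less-used of 5-FU and capecitabine has power of at most about .51 at 7.3 points, and the more-used one between about .51 and .80. The half-sample limit follows from the eligible regimens and needs no assumed mix; the power values are conditional on the unadjusted test and on SD 17.3 for each drug.

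Two stronger readings are not supported. One is that the trial is underpowered for RDI as a whole: the full-sample figure reproduces. The other is that capecitabine is known to be the less-used drug: Protocol 1.2 calls FOLFOX the most common regimen in general, which points that way, but no split for this trial is given and the conclusion does not need one.

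**What to change.** 1. In Protocol 9.3.4, state that .80 power at 7.3 points refers to the full-sample ARDI analysis, with SD 17.3 given as an assumption for ARDI.
2. In the same section, add the detectable difference for 5-FU, capecitabine and oxaliplatin RDI, each from the number of patients per arm whose planned regimen includes that drug. State the SD and whether covariate adjustment is assumed.
3. In SAP 2.1, clarify that ARDI is assessed on all participants and single-drug RDI on participants whose planned regimen includes that drug. Use this one definition in both documents, rather than planned regimen in one place and drug received in the other.

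The cost is wording only. No patients are added, and no analysis or its status changes. The one downside is a less favourable stated power for the single-drug analyses.
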